HPV 9-valent recombinant vaccine (3 milliliters/approximately ½ teaspoon) will be injected into several locations on the tumor surface, using ½ half of the single dose vaccine diluted with saline solution.

If you have cancer of the vulva, the vaccine will be injected without placing the speculum.

Imiquimod cream will be applied to the surface of the tumor at the visit.

You will then receive ½ of the vaccine dose as a subcutaneous shot.

Following the visit, you will receive 6 small doses of imiquimod cream in individual packets. These are to be applied using a vaginal applicator 3 nights per week for the next 2 weeks.

If you have cancer of the vulva, the imiquimod cream will be applied directly on the tumor surface.

You will also receive metformin 500 mg tablets, which are to be taken by mouth twice daily for the next 2 weeks.

A PET/CT test will be performed at treatment completion (week 20), then PET/CT or CT chest/abdomen/pelvis 2 years post treatment. You will have follow-up visits with a physical exam including pelvic exam every 3 months up until 2 years.

Section G: Sample Size/Data Analysis

G1. Sample Size

How many subjects (or specimens, or charts) will be used in this study?

Local: 85 Worldwide: 85

Please indicate why you chose the sample size proposed:

The planned cohort size will be 77 primary cervical cancer patients, the number needed for the evaluation of improvement in time to progression-free survival, with up to 8 vulvar/vaginal cancer patients, since they are rare. Members of the protocol study team have completed a comprehensive review of local control outcomes for all women treated for a locoregionally advanced cervical cancer (bulky FIGO IB3- IVA) with chemoradiotherapy to include standard of care concurrent cisplatin at the Harris Health System. Twenty-four month progression-free survival for patients who presented with FIGO IIIA-IVA cervical cancer is 67%. Since this clinical trial is enrolling an advanced stage cohort, we estimate that PFS would be 67% with standard of care and we will consider the trial a success if PFS is better than 77% at 24 months. Employing a one-sample exponential hazard rate test, and using a survival time of at least 2 years, which is consistent with the follow up time of 2 years, a sample of 77 patients are needed (alpha=10%, one-tailed, history control PFS24 m=67% vs new PDA24m=77%). Similar results are obtained for a standard one-sample log-rank test. .

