Vulvar and vaginal carcinoma patients will be accrued while the trial is enrolling, in addition to the 77 cervical cancer patients, since these cancers are much more rare. An adequate number of patients for statistical comparison is not anticipated to accrue, but this data will be reported separately. Up to 8 vulvar or vaginal cancer patients are anticipated, for a total of 85 patients.

G2. Data Analysis

Provide a description of your plan for data analysis. State the types of comparisons you plan (e.g. comparison of means, comparison of proportions, regressions, analysis of variance). Which is the PRIMARY comparison/analysis? How will the analyses proposed relate to the primary purposes of your study?

The primary objective will be addressed by looking at progression free survival at 24 months compared to a historical cohort with a Kaplan Meyer curve using a log-rank test to evaluate for significance.

Section H: Potential Risks/Discomforts

H1. Potential Risks/Discomforts

Describe and assess any potential risks/discomforts; (physical, psychological, social, legal, or other) and assess the likelihood and seriousness of such risks:

Human Papillomavirus 9-valent Vaccine, Recombinant: The vaccine will be given intratumorally, but this is not anticipated to change the risk compared to standard vaccination, since trial of intralesional injection of HPV vaccine in nearly 1200 women found similar side effects to standard HPV vaccination. There may be some minimal discomfort during vaccine administration. Because vaccines may develop syncope, sometimes resulting in falling with injury, observation for 15 minutes after administration is recommended. Syncope, sometimes associated with tonic-clonic movements and other seizure-like activity, has been reported following HPV vaccination. When syncope is associated with tonic-clonic movements, the activity is usually transient and typically responds to restoring cerebral perfusion by maintaining a supine or Trendelenburg position. ADVERSE REACTIONS The most common ($\geq 10\%$) local and systemic adverse reactions reported: injection-site pain (80-90%), injection-site swelling (23-40.0%), injection-site erythema (17-34.0%) and headache (15%).

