Section L: Cost/Payment

Delineate clinical procedures from research procedures. Will subject's insurance (or subject) be responsible for research related costs? If so state for which items subject's insurance (or subject) will be responsible (surgery, device, drugs, etc). If appropriate, discuss the availability of financial counseling.

Research procedures will be the application of 6 doses of HPV vaccine, requiring a clinic visit with the Gynecologic Oncology provider. These visits and medications will be covered by the institution/trial which is sponsored by the BCM Gynecologic Oncology division. All other visits and imaging are standard of care.

The study medications, including HPV vaccine, metformin and imiquimod, and vaginal applicators (if needed) will be provided at no cost to the study participants. The study sponsor (BCM Division of Gyn Oncology) will be providing these items.

After finishing the treatments, the patient will receive standard follow up care, which includes a PET/CT test about 3 months after treatment completion and follow up visits every 3 months for 2 years that include a physical/pelvic exam and evaluation of symptoms. They will also have a routine CT scan or PET scan (per doctor's preference) at 1 and 2 years after finishing treatment. Insurance will be billed for all standard of care visits and testing, and the patient will be responsible for any co-pays for these visits.

If subjects will be paid (money, gift certificates, coupons, etc.) to participate in this research project, please note the total dollar amount (or dollar value amount) and distribution plan (one payment, pro-rated payment, paid upon completion, etc) of the payment.

Dollar Amount:

0

Distribution Plan:

Section M: Genetics

How would you classify your genetic study?

Discuss the potential for psychological, social, and/or physical harm subsequent to participation in this research. Please discuss, considering the following areas: risks to privacy, confidentiality, insurability, employability, immigration status, paternity status, educational opportunities, or social stigma.

Will subjects be offered any type of genetic education or counseling, and if so, who will provide the education or counseling and under what conditions will it be provided? If there is the possibility that a family's pedigree will be presented or published, please describe how you will protect family member's confidentiality?

Section N: Sample Collection

SAMPLE: Blood

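### G1 uses 77% both as the success threshold and as the design alternative, and does not reconcile that threshold with the 10% test; if applied to observed 24-month PFS, success at a true 77% is about 49%

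*Protocol*

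**What the plan says.** G1 (Sample Size) gives the historical expectation: "we estimate that PFS would be 67% with standard of care". It then states a success criterion: "we will consider the trial a success if PFS is better than 77% at 24 months". The sizing follows: "Employing a one-sample exponential hazard rate test, and using a survival time of at least 2 years", with the result that "a sample of 77 patients are needed (alpha=10%, one-tailed, history control PFS24 m=67% vs new PDA24m=77"%). PDA24m is presumably a slip for PFS at 24 months. G1 adds that a one-sample log-rank test gives similar results. It does not give the power.

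G2 (Data Analysis) says the primary objective is assessed by 24-month PFS "compared to a historical cohort with a Kaplan Meyer curve using a log-rank test to evaluate for significance". It does not mention 77%.

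Three statements bear on follow-up. G1 has "using a survival time of at least 2 years, which is consistent with the follow up time of 2 years". F2 (Procedure) has "A PET/CT test will be performed at treatment completion (week 20), then PET/CT or CT chest/abdomen/pelvis 2 years post treatment". Section L (Cost/Payment) has "follow up visits every 3 months for 2 years that include a physical/pelvic exam and evaluation of symptoms".

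**The concern.** A design alternative and a success threshold do different jobs. The alternative is the true effect at which power is calculated. The threshold is what the data must show. A test of 67% at one-sided 10% becomes significant at an observed value well below the alternative, and that is where its power comes from. If the observed estimate must instead exceed the alternative, the chance of success when the alternative is true is about one half at any sample size.

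G1 gives 77% both jobs in consecutive sentences. If the success sentence is a rule on observed PFS, neither the 10% alpha nor the 67% versus 77% sizing describes it. At stake is how a result somewhat below the planned 77% would be declared: significant under G2, but not a success under G1. In a single-arm trial against a historical control, the pre-stated rule is the main protection against choosing the criterion after seeing the data.

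**Working it through.** **Inputs.** From G1: null PFS24 67%, alternative 77%, one-sided alpha 10%, n = 77 cervical patients. Assumed: exponential PFS (as in G1's sizing test), no dropout, and the follow-up patterns named below.

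**1. The plan's own figure.** Hazard ratio = ln(0.77)/ln(0.67) = 0.2614/0.4005 = 0.653, so |ln HR| = 0.427. With no stated power, 77 cannot be tied to one design. One common formula, using events expected under the null, gives for 80% power n = [(1.2816 + 0.8416)/0.427]² / 0.33 ≈ 75. So 77 is plausible for roughly 80% power. Other variants at exactly 24 months each give 70% to 81%.

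**2. The G1 sentence applied to observed PFS24.** 59/77 = 76.6% fails and 60/77 = 77.9% passes, so success needs at least 60 patients progression-free at 24 months. Exact binomial:
- P(X ≥ 60 | n = 77, p = 0.67) = 0.025
- P(X ≥ 60 | n = 77, p = 0.77) = 0.487

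The same bar at a true 77% with other sample sizes: n = 100 (at least 78), 0.461; n = 150 (at least 116), 0.507; n = 300 (at least 232), 0.478; n = 1000 (at least 771), 0.488. With 77 patients, an 80% chance of success needs a true PFS24 of about 81.0%, and a 90% chance about 82.9%.

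**3. The test that was sized.** One-sample log-rank: Z = (O − E)/√E, reject if Z < −1.2816. With exactly 24 months each and a true 77%, O is expected to be 77 × 0.23 = 17.71 and E = 17.71/0.653 = 27.14. Power ≈ Φ[(27.14 − 17.71 − 1.2816 × √27.14)/√17.71] = Φ(0.65) ≈ 0.74. Normal approximations put the significance cutoff at an observed PFS24 of about 73% to 74%.

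**4. Both rules together.** Simulation, 200,000 trials per scenario. Type I error of the test is about 9.3% throughout. The cap is 24 + 20 × 7/30.4375 = 28.6 months, that is, 2 years after week 20.

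| Follow-up (assumed) | Power at true 77% | Significant but below 60/77 |
|---|---|---|
| Exactly 24 months each | 74% | 25% |
| At least 24 months, capped at 28.6 | 78–79% | 29–30% |
| Until last patient reaches 24 months, 1-year accrual | 80% | 31% |
| Same, 2-year accrual | 84% | 35% |
| Same, 3-year accrual | 87% | 39% |

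The last column is close to power minus 48.7%, because at a true 77% the bar is almost never met without significance (at most about 0.3% of trials). A Wald test on the log exponential hazard gives nearly the same power.

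**The case against.** The strongest reply is that 77% was only ever the target. G1 answers a question about why the sample size was chosen, the success sentence opens with the 67% estimate, and the next sentence reuses the same pair as test inputs. The sentence does not say that the observed estimate must exceed 77%. G2, where the form asks for the primary analysis, has no such bar. On that reading the 49% and the discordance do not apply. This is plausible, and it is why the point is a conflict of wording and not proof of a faulty analysis. But the sentence has the form of a decision rule, and nothing in G1 or G2 withdraws it.

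It is also fair that a clinical bar above the significance cutoff is legitimate, and that this one is conservative: false success falls to about 2.5%. A reader might infer an inflated false-positive risk, but the figures show the opposite. The cost is in missed successes.

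A reader might also infer that the trial has only 49% power, or that 77 patients are too few. The documents do not support that. The 49% belongs to the literal bar, which no sample size would improve. The sized test has about 74% or more.

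Finally, the power depends on follow-up that the protocol does not settle. F2 and Section L suggest that it ends about 2 years after treatment, whereas G1 says at least 2 years. No single power figure, and no single discordance figure, should be quoted without its assumption.

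**Conclusion.** The point holds as an unreconciled success rule that should be fixed. G1 states a threshold equal to its own design alternative, and G2 states a significance test without it. If the G1 sentence is applied to observed 24-month PFS, success is about 2.5% at a true 67% and about 49% at a true 77%; this needs only that all 77 patients have known 24-month status. The range of 25% to 39% for significant results that miss the bar further assumes exponential PFS, no dropout, the one-sample test of G1, and either 24 months each, a 28.6-month cap, or full follow-up with 1 to 3 years of accrual. It does not describe a two-sample log-rank test against the historical cohort, whose size is not given. The arithmetic is firm. Whether the sentence was meant as a rule is not, and only the sponsor can settle that.

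**What to change.** Rewrite the success sentence in G1, for example: *The trial is a success if the one-sided 10% one-sample test rejects a 24-month PFS of 67% in favour of a higher value; 77% is the design alternative, not the success threshold.* State the power beside it, with the accrual and follow-up assumption it rests on.

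If a 77% bar is wanted, keep it explicitly as an added requirement on the observed estimate, and state its own operating characteristics: about 2.5% success at a true 67% and about 49% at a true 77%. Say how a result that is significant but below the bar will be declared.

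Either choice costs one or two sentences in G1, with no extra patients, visits or procedures. It should be made before outcome data are seen.

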Will neonates of uncertain viability or nonviable neonates (as described in 45 CFR 46 Subpart B) be enrolled in the research?

No

E5. Children

Will children be enrolled in the research?

No

Section F: Design/Procedure

F1. Design

Select one category that most adequately describes your research:

u) Drug, Phase II, Single Center

Discuss the research design including but not limited to such issues as: probability of group assignment, potential for subject to be randomized to placebo group, use of control subjects, etc.

This window-of-opportunity study will be offered to all eligible patients undergoing chemoradiation for cervical, vulvar, or vaginal cancer, since it is an additional treatment anticipated to enhance the response to therapy. The treatment group will be compared to a historical control. We will evaluate the immune changes within the tumor microenvironment and validate why the combination immunotherapy study elicited such a robust immune response which led to complete resolution of the cancer, in comparison to the standard of care, chemoradiation. If the combination immunotherapy used together with chemoradiation elicits a more robust antitumor response, there is the potential that the addition of these FDA approved medications to chemoradiation could be a new standard of treatment for squamous cell carcinoma of the cervix and vulva.

Inclusion Criteria:

- Participants must have histologically confirmed locally advanced or metastatic cervical carcinoma (Stage IB2-IVB), vaginal, or vulvar carcinoma (Stage II-IVB), AND not be considered a primary surgical candidate. Patients offered neoadjuvant therapy may be enrolled if they respond and receive chemoradiation. • Participants must have measurable disease, per Recist criteria. See Section 12 (Measurement of Effect) for the evaluation of measurable disease.
- Radiological evaluation shall occur within approximately 30 days prior to enrollment initiation and start of radiation.
- Participants must have an Eastern Cooperative Oncology Group (ECOG) performance status of ≤ 2
- Participants must be ≥ 18 years of age

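### Does G2's log-rank test against a historical cohort need more than the 77 patients that G1 sized for a one-sample test?

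*Protocol*

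**What the plan says.** Protocol, G1 (Sample Size) derives the number of cervical cancer patients. The method is given as "Employing a one-sample exponential hazard rate test, and using a survival time of at least 2 years", the inputs as "alpha=10%, one-tailed, history control PFS24 m=67% vs new PDA24m=77" percent, and the result is that "a sample of 77 patients are needed". The survival time is described as one "which is consistent with the follow up time of 2 years". G1 then adds: "Similar results are obtained for a standard one-sample log-rank test". The 67% comes from the institution's own series, which members of the team "have completed a comprehensive review of local control outcomes for all women treated". The size of that series is not given, and G1 states neither power nor accrual time.

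Protocol, G2 (Data Analysis) describes the primary analysis as "looking at progression free survival at 24 months compared to a historical cohort with a Kaplan Meyer curve using a log-rank test". Protocol, F1 (Design) says only: "The treatment group will be compared to a historical control".

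**The concern.** A one-sample log-rank test compares observed events with the number expected under a reference curve taken as known. A two-sample log-rank test compares two sets of patients and carries the sampling error of both. G2 speaks of a cohort, and G1 shows that the team holds one, so G2 could be read as a two-sample comparison. It does not restate the fixed 67%, the 10% level or the word one-sample.

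If the analysis were run that way, the sample size would belong to a different test. Some of the power behind 77 would be lost, and the loss would be large if the historical series were small. There is also a general worry that a choice left open can be made after the data are seen.

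**Working it through.** **Inputs.** From G1: 24-month PFS of 67% under the null and 77% under the alternative, one-tailed alpha 10%, n = 77, at least 2 years of follow-up. Assumed, because the protocol gives no figure: 80% power, 24 months of uniform accrual, and historical cohorts of M = 77, 300 or 1,000.

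**Effect.** With exponential PFS the monthly hazards are −ln(0.67)/24 = 0.01669 and −ln(0.77)/24 = 0.01089. The hazard ratio is ln(0.77)/ln(0.67) = 0.653, and its logarithm is −0.427.

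**Does 77 belong to a one-sample test?** Events needed on the log-hazard scale are ((1.2816 + 0.8416)/0.427)² = 24.75. With 24 months of accrual plus 24 months of follow-up, the event probability under 77% is 0.322, so n = 24.75/0.322 = 76.8, or 77. G1's figure is therefore recovered from a one-sample test, given the assumed power and accrual. If everyone is followed for exactly 24 months, the event probability is 0.23 and the same formula gives 24.75/0.23 = 107.6.

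**Power of 77 under each reading**, by simulation at one-sided 10% (one-sample 100,000 runs, two-sample 8,000 runs):

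| Follow-up | One-sample log-rank | Two-sample, M = 77 | M = 300 | M = 1,000 |
|---|---|---|---|---|
| Exactly 24 months for all | 74.0% | 54.5% | 67.0% | 71.6% |
| 24-month accrual plus 24 months | 83.8% | 64.6% | 78.2% | 81.5% |

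The loss in percentage points is 19.5, 7.0 and 2.4 in the first row, and 19.2, 5.6 and 2.3 in the second.

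A hand check of the first two-sample entry: the variance of the log hazard ratio is 1/(77 × 0.23) + 1/(77 × 0.33) = 0.0958, with standard error 0.310. Then 0.427/0.310 − 1.2816 is about 0.097, which gives power of about 54%.

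**Which reading does the text support?**

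- G1 and G2 are consecutive answers under one heading, Section G. G1 gives the reference rate, the level and the direction, and closes its derivation with the one-sample log-rank test. A short paragraph later G2 says log-rank test. No other log-rank test is specified in the protocol.
- The G1 form question asks for the number of subjects, specimens or charts. The answer, 85, is fully accounted for by 77 cervical and up to 8 vulvar or vaginal patients. No historical charts are counted.
- J1 (Waiver of Consent) answers that no portion of the research needs a waiver. A pooled patient-level analysis would use past patients' charts.
- The chart review is described as finished, and G1 uses it only to supply a rate.

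None of this excludes a two-sample test, since the review could sit under another approval. It does make the one-sample reading the natural one, and on that reading the loss is zero.

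**The case for a change.** The best case for a change is that G2 is the protocol's only statement of the primary analysis, and its form asks which comparison is primary. In a single-arm trial, whether the reference is fixed or estimated is a basic design choice. G2's wording can fit both tests, and their error properties differ. A clarification would cost one line and no patients.

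Part of this stands. G2 is terse, the two-sample reading cannot be ruled out from the wording alone, and a cross-reference to G1 would do no harm. What does not stand is the step from terse to defective. G2 says nothing false and does not contradict G1, and the missing specification is in the section just before it.

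Two further arguments belong elsewhere:

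- If the 67% was estimated from 77, 300 or 1,000 patients, the one-sample test's true type I error would be about 17–19%, 12–13% or 10–11%. That follows from using any fixed historical benchmark and would remain however clearly G2 were worded.
- G1's remark about success if PFS exceeds 77% is not a log-rank rule of either kind. It does not help decide which log-rank test G2 means.

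**Conclusion.** The concern does not call for a change. G2 omits the word one-sample, the 67% and the 10% level, but G1 supplies all three, and analysts or a statistical analysis plan would complete G2 accordingly. Under that reading 77 patients are matched to the test used and nothing is lost.

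The loss of about 2 to 20 points arises only if a two-sample test is really meant. Its size is set by a historical cohort of 77 to 1,000 patients, which is assumed here, and the second row of power figures also assumes the accrual period. G1 states no power, so no stated target is missed. Only evidence that a two-sample comparison is actually intended would alter this conclusion. The historical cohort's size and the power of 77 for that test would then have to be given.
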